10.3.4 Assessment of Severity

The Investigator will make an assessment of severity for each AE, and this should be recorded on the CRF or SAE form according to the following categories:

Mild: an event that is easily tolerated by the study participant, causing minimal discomfort, and not interfering with everyday activities.

Moderate: an event that is sufficiently discomforting to interfere with normal everyday activities

Severe: an event that prevents normal everyday activities.

*The term 'severe' used to describe the intensity of an event should not be confused with the term 'serious', as defined in section 10.1, which is a regulatory definition based on study participant/event outcome action criteria. For example, a headache may be severe but not serious, while a minor stroke may be serious but is not severe.

10.4 REPORTING SAEs TO THE SPONSOR (University of Edinburgh and NHS Lothian)

Any AE that is assessed as an SAE is subject to expedited reporting requirements to the Sponsor. The SAEs described in 10.2.1 do not require expedited reporting to the sponsor. The Investigator is responsible for reporting SAEs to ACCORD within 24 hours of becoming aware of the event.

SAE reports will be emailed as a .pdf file to [contact] SAE reports will be complete as far as possible and will be signed and dated by the Investigator. The SAE does not require to maintain blinding as this is an unblinded trial. The Research Governance Coordinator, or designee, will complete and return the Cover Sheet and Return Receipt or send an email to confirm receipt of the SAE report within 1 working day. If this email is not received within 1 working day of sending the report to ACCORD, the Investigator must email [contact] to check that the report has been received by ACCORD.

All copies of SAE reports emailed to ACCORD, and any follow-up information and correspondence will be kept by the Investigator in the Investigator Site File (ISF) and by the Sponsor in the Sponsor File or Trial Master File (TMF).

ACCORD will report SAEs, as required, to the Chief Investigator/Trial Manager upon request.

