10.1.3 Transfusion Related Adverse Reaction (AR) or Event

Any untoward and unintended response to a transfused blood component.

10.1.4 Serious Adverse Event (SAE) or Serious Adverse Reaction (SAR) OR Serious Transfusion Related Adverse Reaction

A serious adverse event (SAE) is defined as an untoward occurrence that:

- results in death.
- is life-threatening.
- requires hospitalisation or prolongation of existing hospitalisation.
- results in persistent or significant disability or incapacity.

An SAE occurring to a research participant should be investigated at a local level by the local PI and then reported to the CI and sponsor when, in the opinion of the local PI, the event was either

- Related it resulted from administration of any of the research procedures And / or
 - Unexpected the type of event is not listed in the protocol as an expected occurrence.

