10.2 IDENTIFYING AND REPORTING AEs AND SAEs

10.2.1 Assessment of Transfusion Reactions

As mentioned above, transfusion related reactions will be assessed in accordance with the definitions and imputability as set out by SHOT but will also be recorded as an AE on the trial database. All Serious Transfusion Related Adverse Reactions will be recorded as part of the trial data collection process.

Examples include:

- Incorrect or incompatible blood transfusion
- Serious adverse reactions to blood transfusion including (but not exclusively):
- Allergic/febrile transfusion reactions occurring at any time up to 24 hours following a transfusion of a blood component
- Acute or delayed Haemolytic transfusion reaction
- Post transfusion Purpura (thrombocytopenia)
- Transfusion associated graft vs host disease
- Transfusion associated circulatory overload
- Transfusion associated dyspnoea
- Transfusion associated acute lung injury
- Transfusion transmitted infection

IRAS 299977/308830

Version 5.0 26Jun2024

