10.2.2 AEs and SAEs that do not require reporting

This study enrols older, anaemic participants who have undergone major emergency surgery and it is expected that many of these participants will suffer medical complications, with consequences up to and including death. Only complications considered by the local PI, or delegated authority, to be *related to the use of study procedures* and not a typical and frequently reported complication of admission to hospital with hip fracture should be reported as AEs. Complications that fall into this category but are defined as endpoint events in protocol section 1.4, e.g. cardiac events, will be recorded as outcome events (whether they are deemed to be related to the use of study procedures or not). Common hospital complications of hip fracture are listed in the table below:

Common complications of admission to hospital with hip fracture
Electrolyte disturbance, including, but not limited to hypo or hypernatremia, hypo or
hyperkalaemia.
Anaemia*
AKI
Delirium*, acute confusional state
Cognitive impairment, chronic or acute
Venous thromboembolic Disease
Respiratory: Chest infection pneumonia, sepsis
Cardiac*: myocardial infarction, acute coronary syndrome, atrial fibrillation, another arrhythmia, *
Cerebrovascular: Stroke or transient ischaemic attack
Infection*
Urinary infection
Pressure sores
Skin ulcers
Immobility
Fall
Death
Complications of surgical fixation of fractured hip
Wound complications
Impaired wound healing
Haematoma
Mechanical malfunction [dislocations, cutting-out, refracture]
Infections
non/malunion

* Complications that are recorded as part of the outcome measures are detailed in the protocol.

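### Section 10.4 exempts serious transfusion reactions from expedited sponsor reporting, apparently through a wrong cross-reference, and does not square with section 10.1.4

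*Protocol*

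**What the plan says.** Four parts of chapter 10 of the Protocol bear on this.

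- **Section 10.4** opens with a general rule: "Any AE that is assessed as an SAE is subject to expedited reporting requirements to the Sponsor". It then gives the exception, "The SAEs described in 10.2.1 do not require expedited reporting to the sponsor", and after that the clock: "The Investigator is responsible for reporting SAEs to ACCORD within 24 hours of becoming aware of the event".
- **Section 10.2.1**, the target of the exception, is headed "10.2.1 Assessment of Transfusion Reactions". Its examples include incompatible transfusion, haemolytic reaction, circulatory overload, acute lung injury and transfusion-transmitted infection. They are to be assessed against the SHOT definitions and entered as adverse events on the trial database, and "All Serious Transfusion Related Adverse Reactions will be recorded as part of the trial data collection process". No time limit for telling the sponsor is given.
- **Section 10.2.2** is headed "AEs and SAEs that do not require reporting". It lists the usual complications of a hip-fracture admission and keeps as reportable only those events that are both related to study procedures and not typical of such an admission. Section 10.4 does not mention it.
- **Section 10.1.4** says that a serious event is to be investigated locally and then "reported to the CI and sponsor when, in the opinion of the local PI, the event was either" related to the research procedures, unexpected, or both.

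**The concern.** The exception in 10.4 falls on the class of serious harm most directly tied to the intervention. Section 1.2.3 defines the intervention as red cell transfusion by haemoglobin trigger, and under section 5.2.1 liberal-arm participants are to receive a unit soon after randomisation, while restrictive-arm participants wait for a lower trigger. Exposure to transfusion, and so to its reactions, is expected to differ by arm.

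A site that follows 10.4 to the letter would record a serious reaction but would not be obliged to send it to the sponsor within 24 hours, and no other time limit is stated for it. The protocol plans no interim analysis (section 9.2) and no early stopping rules (section 4.2.4), so delay in individual reports has some weight. A site that follows 10.1.4 would report the same event to the sponsor. Practice could therefore vary between sites.

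**Working it through.** No arithmetic applies, and there is no figure in the plan to reproduce. The check is to follow two events through the text.

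**Event A: a serious haemolytic reaction to a unit given because of the allocated trigger.**

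| Section | Instruction for event A | Stated time limit to sponsor |
|---|---|---|
| 10.1.4 | Serious. If the local PI judges it related, investigate and report to the chief investigator and sponsor | None |
| 10.2.1 | Assess against SHOT; record as an adverse event and in the trial data | None |
| 10.2.2 | Not among the listed complications; if related to study procedures, it stays reportable | None |
| 10.4, general rule | Expedited reporting | 24 hours |
| 10.4, exception | Expedited reporting not required | Removed |

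Event A is reportable to the sponsor under 10.1.4 but is taken off the only serious-event route that has a clock.

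**Event B: a serious chest infection that the local PI thinks unrelated.** Section 10.2.2 lists it as a usual complication and keeps it out of adverse event reporting. It does not need the exception in 10.4 to escape the 24-hour rule, although the opening sentence of 10.4 does not say so.

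**Which target was meant?** Three things point to a slip.

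1. The heading of 10.2.2 describes what an exemption clause would be expected to point to; the heading of 10.2.1 does not.
2. Other cross-references in the protocol are wrong. Section 10.3.1 sends the reader to section 11.1 for the definition of seriousness, but 11.1 concerns inspection of records and the definition is in 10.1.4. Section 6.2 cites a section 4.2.2.3 that does not exist; the matter is in 4.2.3.3.
3. The intervention's own serious reactions are an unlikely class to exempt without a stated reason, and none is given.

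**Does expectedness resolve it?** Appendix B lists transfusion reactions as expected. Under 10.1.4 being related is enough on its own, because the two criteria are joined by and/or. An expected reaction that is related is still reportable.

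**The case against.** The strongest reply is that the exemption may be deliberate. Section 10.2.2 already removes its own events, so the serious events that would need a separate carve-out in 10.4 are the transfusion reactions. Section 10.2.1 gives these their own route through SHOT assessment and trial data, and Appendix B calls them expected. This stands as a possibility: that 10.2.2 was the intended target is an inference.

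A second reply is that 10.1.4 sets no timeline and 10.4 lifts only the expedited requirement, so both could hold if related reactions reached the sponsor more slowly. That is logically possible, but chapter 10 describes no such slower route and gives it no time limit. The chapter does place reporting under a sponsor procedure (CR006), which may contain one and is not reproduced in the protocol.

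Two stronger readings are tempting and are not supported.

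- A reader might infer that the wrong reference leaves the usual hip-fracture complications, deaths included, under the 24-hour rule. Section 10.2.2 filters these out first and sends endpoint events to outcome recording, so this largely falls away.
- A reader might infer that expedited reporting is the trial's principal safeguard. Section 11.6 sets up an independent data monitoring and ethics committee to oversee safety, section 10.2.4 requires timely logging of adverse events, and section 13.5 lets the investigators or co-sponsors end the study at any time. The reactions are recorded, so they are not lost to the analysis.

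**Conclusion.** The point holds as an inconsistency in the safety-reporting rules that the sponsor should resolve. As written, 10.4 removes the stated 24-hour clock from serious transfusion reactions, puts nothing in its place, and does not explain how this fits with 10.1.4. That is so whether the reference is a slip or intended. A slip is the likelier explanation but is not proven.

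The size can be given only as exposure. The rule applies to every serious transfusion reaction in either arm, and up to 563 liberal-arm participants are assigned at least one unit. That is a count of people exposed, not of reactions, and the protocol gives no reaction rate from which to estimate events. The consequence is possible delay to the sponsor, not loss of data. The sample size and the primary analysis are untouched.

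The conclusion assumes that a reaction to a unit given under the allocated trigger can be judged related in the sense of 10.1.4, and that CR006 does not already impose a time limit on these events.

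**What to change.** Reconcile section 10.4 with sections 10.1.4, 10.2.1 and 10.2.2, starting with a statement from the sponsor of what was intended.

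- If the reference is a slip, change it in 10.4 to 10.2.2, so that related serious transfusion reactions stay under the 24-hour route.
- If the exemption is intended, say so in 10.4, give the reason, state how and by when these reactions reach the sponsor, and align 10.1.4 with it.

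In either case, make one pass through the adverse event log for serious transfusion reactions that were not sent to the sponsor. There is no evidence in the protocol that any were missed; the check simply closes the question.

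The cost is a small amendment, a note to sites and the log check.

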11 OVERSIGHT ARRANGEMENTS

11.1 INSPECTION OF RECORDS

Investigators and institutions involved in the study will permit trial related monitoring and audits on behalf of the sponsor, REC review, and regulatory inspection(s). In the event of audit or monitoring, the Investigator agrees to allow the representatives of the sponsor direct access to

> CR007-T02 v0.5 Page **48** of **69**

IRAS 299977/308830

Version 5.0 26Jun2024

all study records and source documentation. In the event of regulatory inspection, the Investigator agrees to allow inspectors direct access to all study records and source documentation.

11.2 STUDY MONITORING AND AUDIT

The ACCORD Sponsor Representative will assess the study to determine if an independent risk assessment is required. If required, the independent risk assessment will be carried out by the ACCORD Quality Assurance Group to determine if an audit should be performed before/during/after the study and, if so, at what frequency.

Risk assessment, if required, will determine if audit by the ACCORD QA group is required. Should audit be required, details will be captured in an audit plan. Audit of Investigator sites, study management activities and study collaborative units, facilities and 3rd parties may be performed.

11.3 PUBLIC ENGAGEMENT

A patient Personal and Public Involvement (PPI) representative is a co-applicant and will attend the trial management group throughout the trial to ensure the views and opinions of service users, carers and the public are represented. In addition, a wider PPI group will be consulted on the protocol prior to submission for ethical approval, and specifically will be asked to review patient and patient-representative materials including the Patient (or representative) Information Leaflet and consent forms.

The views of PPI representatives will be sought during interpretation of the study results as appropriate.

11.4 TRIAL MANAGEMENT GROUP

The trial will be coordinated by a Trial Management Group, consisting of selected grant holders, a trial manager and trial nurse.

The Trial Manager will oversee the study and will be accountable to the Chief Investigator. The Trial Manager will be responsible for checking the CRFs for completeness, plausibility, and consistency. Any queries will be resolved by the Investigator or delegated member of the trial team.

A Delegation Log will be prepared for each site, detailing the responsibilities of each member of staff working on the trial.

11.5 TRIAL STEERING COMMITTEE

A Trial Steering Committee (TSC) will be established to oversee the conduct and progress of the trial and advise the investigators as required. The TSC will include an independent Chair, at least one independent clinician, at least one independent methodologist, and at least one independent PPI representative. The terms of reference of the Trial Steering Committee, the draft template for reporting, and the names and contact details are detailed in CR015 DMEC & TSC Charters.

IRAS 299977/308830

Version 5.0 26Jun2024

11.6 DATA MONITORING AND ETHICS COMMITTEE

An independent Data Monitoring and Ethics Committee (DMEC) will be established to oversee the safety of participants in the trial. The DMC will comprise three individuals and include at least one statistician and one clinical content expert. The terms of reference of the Data Monitoring Committee and the names and contact details are detailed in CR0015 DMEC & TSC Charters.

The DMEC Charter will be signed by the appropriate individuals prior to the trial commencing.

12 GOOD CLINICAL PRACTICE

12.1 ETHICAL CONDUCT

The study will be conducted in accordance with the principles of the International Conference on Harmonisation Tripartite Guideline for Good Clinical Practice (ICH GCP). Before the study can commence, all required approvals will be obtained, and any conditions of approvals will be met.

12.2 INVESTIGATOR RESPONSIBILITIES

The Investigator is responsible for the overall conduct of the study at the site and compliance with the protocol and any protocol amendments. In accordance with the principles of ICH GCP, the following areas listed in this section are also the responsibility of the Investigator. Responsibilities may be delegated to an appropriate member of study site staff.

12.2.1 Informed Consent

The Investigator is responsible for ensuring informed consent is obtained before any protocol specific procedures are carried out. The decision of a participant to participate in clinical research is voluntary and should be based on a clear understanding of what is involved.

Participants must receive adequate oral and written information – appropriate Participant Information and Informed Consent Forms will be provided. The oral explanation to the participant will be performed by the Investigator or qualified delegated person and must cover all the elements specified in the Participant Information Sheet and Consent Form.

The participant must be given every opportunity to clarify any points they do not understand and, if necessary, ask for more information. The participant must be given sufficient time to consider the information provided. It should be emphasised that the participant may withdraw their consent to participate at any time without loss of benefits to which they otherwise would be entitled.

The participant will be informed and agree to their medical records being inspected by regulatory authorities and representatives of the sponsor(s).

The Investigator or delegated member of the trial team and the participant will sign and date the Informed Consent Form(s) to confirm that consent has been obtained. The participant will

CR007-T02 v0.5 Page **50** of **69**

IRAS 299977/308830

Version 5.0 26Jun2024

receive a copy of this document and a copy filed in the Investigator Site File (ISF) and participant's medical notes (if applicable).

12.2.2 Study Site Staff

The Principal Investigator must be familiar with the protocol and the study requirements. It is the Principal Investigator's responsibility to ensure that all staff assisting with the study are adequately informed about the protocol and their trial related duties.

12.2.3 Data Recording

The Principal Investigator is responsible for the quality of the data recorded in the CRF at each Investigator Site.

12.2.4 Investigator Documentation

The Principal Investigator will ensure that the required documentation is available in local Investigator Site files (SFs.)

12.2.5 GCP Training

For non-CTIMP (i.e., non-drug) studies all researchers are encouraged to undertake GCP training to understand the principles of GCP. However, this is not a mandatory requirement unless deemed so by the sponsor. GCP training status for all investigators should be indicated in their respective CVs.

12.2.6 Confidentiality

All laboratory specimens, evaluation forms, reports, and other records must be identified in a manner designed to maintain participant confidentiality. All records must be kept in a secure storage area with limited access. Clinical information will not be released without the written permission of the participant. The Investigator and study site staff involved with this study may not disclose or use for any purpose other than performance of the study, any data, record, or other unpublished information, which is confidential or identifiable, and has been disclosed to those individuals for the purpose of the study. Prior written agreement from the sponsor or its designee must be obtained for the disclosure of any said confidential information to other parties.

12.2.7 Data Protection

All Investigators and study site staff involved with this study must comply with the requirements of the appropriate data protection legislation (including the General Data Protection Regulation and Data Protection Act) about the collection, storage, processing and disclosure of personal information.

Computers used to collate the data will have limited access measures via usernames and passwords.

CR007-T02 v0.5 Page **51** of **69**

IRAS 299977/308830

Version 5.0 26Jun2024

Published results will not contain any personal data and be of a form where individuals are not identified, and re-identification is not likely to take place

13 STUDY CONDUCT RESPONSIBILITIES

13.1 PROTOCOL AMENDMENTS

Any changes in research activity, except those necessary to remove an apparent, immediate hazard to the participant in the case of an urgent safety measure, must be reviewed and approved by the Chief Investigator.

Amendments will be submitted to a sponsor representative for review and authorisation before being submitted in writing to the appropriate REC, and local R&D for approval prior to participants being recruited into an amended protocol.

13.2 MANAGEMENT OF PROTOCOL NON-COMPLIANCE

Prospective protocol deviations, i.e., protocol waivers, will not be approved by the sponsors and therefore will not be implemented, except where necessary to eliminate an immediate hazard to study participants. If this necessitates a subsequent protocol amendment, this should be submitted to the REC, and local R&D for review and approval if appropriate.

13.2.1 Definitions

A protocol **deviation** is any change, divergence, or departure from the study design, procedures defined in the protocol or GCP that does not significantly affect a subject's rights, safety, or well-being, or study outcomes.

A protocol **violation** is a deviation that may potentially significantly impact the completeness, accuracy, and/or reliability of the study data or that may significantly affect a subject's rights, safety, or well-being.

For the purpose of the trial, any non-compliance with the allocated RBC transfusion intervention, such as failure to transfuse in response to a trigger Hb and/or administering transfusion when the Hb concentration does not indicate transfusion, should be reported as a protocol deviation. For transfusion decisions, a deviation will be defined as failure to follow the allocated transfusion intervention following an Hb measurement within 48 hours following the Hb measurement.

In the restrictive group, any transfusions administered when the Hb is >75g L⁻¹ will be reported as a deviation.

The following scenarios are protocol deviations of particular interest.

1. Transfusion of red blood cells at Hb above the predefined transfusion trigger.

IRAS 299977/308830

Version 5.0 26Jun2024

- 2. Failure to transfuse within 48 hours after the protocol requires a red cell transfusion according to the allocated trial group.
- 3. Transfusion without checking haemoglobin level.
- 4. Major haemorrhage: It may be necessary for physicians to transfuse participants with red blood cells in emergency or life-threatening situations, for example in a major haemorrhage or uncontrolled bleeding. These transfusions will be recorded together with the reasons for the transfusion.

